12. STATISTICS

12.1 Statistical and Analytical Plans

Clinical data collected throughout the study will be analyzed by descriptive statistics to assess the study objectives. Descriptive statistics will be provided in summary tables according to the type of variable summarized:

- Quantitative variables will be summarized by using n (sample size), arithmetic mean, standard deviation (SD), median, minimum and maximum.
- Categorical variables will be summarized by using frequency distribution and percentages.

The design of the proposed study does not involve randomization, so no pre-defined subgroups of subjects are planned to be enrolled.

For time-to-event variables, cumulative freedom from event will be evaluated using Kaplan-Meier (KM)

method. The degree of uncertainty will be expressed with 95% confidence limits (calculated per the method proposed by Greenwood). KM graphs will be presented along with the number of case-at-risk at exact time points.

Unless otherwise specified, the significance level used for other statistical testing (for descriptive purposes) will be 0.05 and two-sided tests will be used.

The Statistical Analysis Plan (SAP) could be issued before database lock with more technical and detailed elaboration of the principal features of statistical analyses. Any deviations from the original statistical plan (including unplanned analyses) will be documented in the Clinical Study Report.

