12.2.2 Evaluation of Efficacy

The first efficacy endpoint (Bone union achievement) will be analyzed reporting the number and the proportion of procedures with bone union achieved (Success) together with the relative 95% confidence interval.

The second efficacy endpoint (Post-treatment fracture-free survival) will be analyzed reporting the number and the proportion of procedures with fracture(s) occurred in the treated bone up to 1 year follow-up together with the relative 95% confidence interval.

The cumulative freedom from fracture will be also evaluated using Kaplan-Meier (KM) method, the degree of uncertainty will be expressed with 95% confidence limits (calculated per the method proposed by Greenwood) and a KM graph will be presented along with the number of case-at-risk at exact time points.

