14 STATISTICAL ANALYSIS METHODS

The methods of analysis to be used for both objectives of the study and for description of the study variables are detailed below.

Quantitative variables will be described with measures of central tendency and dispersion: mean, median, SD (standard deviation), Q1 (first quartile) and Q3 (third quartile), minimum and maximum. Qualitative variables will be described using absolute and relative frequencies.

In the descriptive analysis of qualitative variables, two percentage columns will be presented, total percentage (%) and valid percentage (% valid), that are respectively, the percentage over the sum of valid responses plus missing values and the percentage over the total of valid responses.

Clopper-Pearson confidence intervals at 95.0% will be shown for the primary and secondary objectives.

For time-to-event variables (i.e. fracture free-survival) will be analysed using the Kaplan-Meier method. The median and the 95% CI as well as the number of events and patients censored will be provided. Error standard will be estimated per the method Greenwood (Greenwood, 1926). KM graphs will be presented along with the number of case-at-risk at exact time points.

Change in Gillette Functional Assessment Questionnaire from Screening to 1 year follow up will be analysed by means of descriptive statistics as a continuous variable. Comparisons will be performed by means of paired t-test (parametric) or Wilcoxon (non-parametric) depending on the distribution of the sample.

These tests will be used in all bilateral cases and with a level of significance of 0.05. In cases where a p-value less than 0.05 appears, it refers to the existence of statistical significance.

No imputation for missing data will be considered.

No adjustment for multiple comparisons will be performed.

Data will be analysed using SPSS v29.0 or later.

Interim Analysis: No interim analysis is planned.

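### The Kaplan-Meier limits for freedom from fracture name Greenwood but no scale and no zero-event rule; read literally they are poor for about 20 nails (minor)

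*Protocol*

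**What the plan says.** Protocol 12.1 sets the general rule for time-to-event variables: "The degree of uncertainty will be expressed with 95% confidence limits (calculated per the method proposed by Greenwood". Protocol 12.2.2 repeats it for the fracture endpoint, after giving the crude proportion with its own 95% interval: "The cumulative freedom from fracture will be also evaluated using Kaplan-Meier (KM) method".

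SAP 14 attaches Greenwood to the standard error only: "Error standard will be estimated per the method Greenwood (Greenwood, 1926". For Kaplan-Meier output it lists this: "The median and the 95% CI as well as the number of events and patients censored will be provided". SAP 24.3 repeats that list and adds numbers at risk. It names no limit for the one-year value.

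For the crude proportions the SAP chooses an exact method: "Clopper-Pearson confidence intervals at 95.0% will be shown for the primary and secondary objectives".

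Neither document states a transformation for the Kaplan-Meier limits or a rule for a sample with no fractures.

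**The concern.** Greenwood's formula gives a variance. Turning it into limits also needs a scale, and with about 20 nails and a fracture-free proportion expected to be high, the scale matters. The literal reading of protocol 12.1 and 12.2.2 is the untransformed interval. Without censoring this equals the simple normal-approximation binomial interval, which the SAP avoids for the crude proportion.

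Fracture-free survival is one of two performance endpoints. Protocol 6.2 intends a visual comparison with other devices, and protocol 5.2 ties the study to confirming benefit/risk and keeping the CE mark. For that use the lower limit is what counts, and a lower limit that is too high flatters the device. If the scale is simply left open, it could be chosen after the data are seen.

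**Working it through.** **Inputs**
- Evaluable nails: 20 (protocol 7.2). Enrolled: about 25, with 20% lost or not evaluable (protocol 12.3).
- Fracture risk: 11.11% to 37.29%, the repeat-fracture row in protocol 11.1.6. That table gives no time point, so its use as one-year risk is an assumption.
- Confidence level: 95%, two-sided.
- Nails are treated as independent. Protocol 12.3 allows 1 to 4 procedures per child and gives no within-child correlation.

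**The plan's own figures.** The documents give no width or coverage for the Kaplan-Meier interval. Their sample-size figures reproduce where a criterion is stated. At a 31% rate the exact upper limit is 60.5% for 14 procedures and 59.4% for 15, so 15 is the smallest number meeting 60%. Also 20/(1 − 0.20) = 25.

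**Literal interval.** Without censoring before one year, Greenwood's standard error for the fracture-free estimate S reduces to √(S(1 − S)/n). With one fracture in 20 nails, SE = √(0.95 × 0.05/20) = 0.04873 and 1.96 × SE = 9.55 points, giving 85.4% to 104.6%.

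**Log-log interval.** The limits are S^exp(±1.96 × SE/(S·|ln S|)). For the same case SE/(S·|ln S|) = 0.04873/(0.95 × 0.05129) ≈ 1.00 and exp(1.96) = 7.10. Then 0.95^7.10 = 69.5% and 0.95^(1/7.10) = 99.3%. With no fractures ln S = 0, so this scale fails too. The exact lower limit there is 0.025^(1/20) = 83.2%.

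| Fractures of 20 | Literal | Log-log | Exact (crude proportion) |
|---|---|---|---|
| 0 | 100–100% | 100–100% | 83.2–100% |
| 1 | 85.4–104.6% | 69.5–99.3% | 75.1–99.9% |
| 2 | 76.9–103.1% | 65.6–97.4% | 68.3–98.8% |
| 3 | 69.4–100.6% | 60.4–94.9% | 62.1–96.8% |
| 4 | 62.5–97.5% | 55.1–92.0% | 56.3–94.3% |

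**How often this happens.** Limits above 100% need 1 to 3 fractures. The binomial probability is 73% at a risk of 11.11%, 40% at 20%, 22% at 25% and 3% at 37.29%. No fractures has probability (1 − 0.1111)^20 = 9.5% at 11.11%, 1.2% at 20%, and about 0% at 37.29%.

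**Coverage, n = 20, exact binomial enumeration**

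| Risk | Literal | Log-log alone | Log-log + exact rule at zero |
|---|---|---|---|
| 11.11% | 90.1% | 84.2% | 93.7% |
| 15% | 81.9% | 93.9% | 97.8% |
| 20% | 92.1% | 95.6% | 95.6% |
| 25% | 89.5% | 95.6% | 95.6% |
| 30% | 94.7% | 95.1% | 95.1% |
| 37.29% | 93.9% | 96.0% | 96.0% |
| Mean over range | 91.0% | 94.6% | 95.8% |
| Minimum over range | about 81% | 84.2% | 92.3% |

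**Direction of the misses.** Averaged over the range, the literal lower limit lies above the true fracture-free rate in 7.4% of studies (17.6% at a risk of 15%, 9.1% at 25%) against a nominal 2.5%. That is most of the 9.0% total miss rate. With log-log and the exact rule it is 0.5%.

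**Planned set with censoring.** The implant analysis set holds all nails, so the realistic case is 25 nails with 20% censored. Simulated coverage of the literal interval is 92.1%, 90.9%, 92.1% and 92.5% at risks of 11.11%, 20%, 24.2% and 37.29%.

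**The case against.** The strongest reply is that the plan never says plain scale. SAP 14 ties Greenwood to the standard error alone, and the same variance underlies log and log-log limits. This stands: a reader might infer that the plan prescribes the untransformed interval, but the documents show only that the scale is unstated and that the literal reading leads there.

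Second, zero width is not peculiar to the plain scale, and comparing the plain interval with log-log plus an added rule is unequal. This also stands in part. At a risk of 11.11%, log-log alone covers less (84.2%) than the plain interval (90.1%), and giving the plain interval the same exact rule raises it to 90.1% + 9.5% = 99.6%. The scale still matters elsewhere. At 15% the rule lifts the plain interval only to 81.9% + 3.9%, about 86%, against 97.8%. At 20% and above it adds nothing, because the exact zero-fracture interval (83.2% to 100%) does not contain a true value of 80% or less.

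Third, the exact interval for the crude fracture proportion already carries the endpoint, protocol 12.2.2 adds the curve as a further display, and the only Kaplan-Meier interval the SAP lists goes with the median. If 63% to 89% are fracture-free at one year, that median will probably not be reached. All this limits the consequence. It does not remove the protocol's commitment to limits on cumulative freedom from fracture.

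**Conclusion.** The point holds as a minor one. The plan omits the scale and a zero-event rule for its Kaplan-Meier limits. On the literal reading, 20 uncensored nails give impossible upper limits with 1 to 3 fractures and no width with none. Coverage averages about 91% (about 81% to 95%), or about 91% to 93% with 25 nails and 20% censored. The error mostly favours the device. The report could also show two discordant intervals for one endpoint: with 1 fracture in 20, 75.1–99.9% exact beside 85.4–104.6% from the curve.

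A reader might conclude that coverage is far below 95% throughout. The figures do not support that: the average shortfall is about 4 points, and coverage is 94.7% at a risk of 30% and 93.9% at 37.29%. Nor is the endpoint's main reporting compromised, since the effect is confined to a supplementary display with no decision rule.

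The figures rest on reading the 11.11% to 37.29% range as one-year risk and on independent nails. With several nails per child, true coverage of any of these intervals could be lower, by an amount the documents do not allow one to calculate.

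**What to change.** In protocol 12.1 and 12.2.2 and SAP 14 and 24.3, state that the 95% limits for Kaplan-Meier freedom from fracture, including the one-year value and the bands on the graph, use Greenwood's variance on the complementary log-log scale. Add that if no fracture occurs the exact lower limit 0.025^(1/n) is reported, with n the number of nails fully followed (83.2% for 20). Both parts are needed, because log-log alone is degenerate at zero fractures.

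The cost is small and changes no endpoint or data collection. Lower limits will fall, most visibly with a single fracture (85.4% to 69.5% at 20 nails, somewhat below the exact 75.1%), so the two intervals will be closer in character but not identical. On software the SAP says: "Data will be analysed using SPSS v29.0 or later". The documents do not show whether that package outputs this scale, so a short script may be needed.

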12.1.1 Population(s) of analysis

The following populations will be defined:

- The Full Analysis Set (FAS) population will consist of all enrolled patients treated by the means of JTIN application and who didn't oppose to study participation. The FAS population will be used for all the analyses of the study that are presented at subject level.
- The Full Analysis Implant Set (FAIS) population will consist of all JTIN applications performed on subjects belonging to the FAS population. The FAIS population will be used for all the analyses of the study that are presented at implant level.

12.1.2 Efficacy, Safety and Other Variables

12.1.2.1 Efficacy Variables

Efficacy variables will include:

1. Bone union achievement;
2. Post-treatment fracture free survival.

12.1.2.2 Safety Variables

Safety variables will include:

1. Any complications;
2. Re-operation/Revision;
3. Implant survival;
4. Any expected/unexpected AE (see Section 11.1.5 for details).

12.1.2.3 Other Variables

All variables reported in the Table above (Section 4.1) will be included, as per scheduling assessment.

12.2 Statistical Evaluation

12.2.1 Evaluation of Safety

To evaluate the primary safety objective of the analysis, the number of all AEs, SAEs and MDDs and the number and the percentage of implants with subsequent AEs, SAEs and MDDs will be summarized (primary endpoint), together with the information about relationship (certainly or possibly related) to JTIN.

In addition, a similar analysis will be performed at subject level (number and percentage of subjects with at least one implant with subsequent adverse events).

Furthermore, as secondary safety endpoint, the implant survival rate will be evaluated and reported as percentage of implants with no exchanged nails up to 1 year follow-up.

12.2.2 Evaluation of Efficacy

The first efficacy endpoint (Bone union achievement) will be analyzed reporting the number and the proportion of procedures with bone union achieved (Success) together with the relative 95% confidence interval.

The second efficacy endpoint (Post-treatment fracture-free survival) will be analyzed reporting the number and the proportion of procedures with fracture(s) occurred in the treated bone up to 1 year follow-up together with the relative 95% confidence interval.

The cumulative freedom from fracture will be also evaluated using Kaplan-Meier (KM) method, the degree of uncertainty will be expressed with 95% confidence limits (calculated per the method proposed by Greenwood) and a KM graph will be presented along with the number of case-at-risk at exact time points.

12.2.3 Exploratory Analyses

Change in Gillette Functional Assessment Questionnaire from Screening to bone consolidation assessment visit and to 1 year follow up will be analyzed by means of

descriptive statistics as a continuous variable. Pre-post comparisons will be performed by means of paired t-test.

12.3 Determination of the Sample Size

Due to the observational nature of the study, no formal sample size calculation has been done, but a revision of the literature on the complication rates (intended as at least one serious/not serious adverse event certainly or possibly related to the procedure up to 1 year follow-up) has been made. The scientific literature reports that the percentage of procedures which develop at least one serious/not serious adverse event certainly or possibly related to the procedure itself is between 9% and 60%, with a mean of 31%. Assuming a complication rate aligned or better than the mean observed in literature (31%), a sample size of 15 procedures will be sufficient to estimate the adverse event rate with the upper limit of the 95% confidence interval equal or lower than the worst complication rate seen in literature (i.e. 60%).

Starting from this sample size, to also assume that the success rate (intended as proportion of procedures that result in a bone union achieved) is aligned or better than the mean observed in literature (80%), 20 procedures will be needed.

Considering a drop-out or a non-evaluable rate of 20% of the procedures, a total of approximately 25 procedures should be made. Each subject could have from 1 to 4 procedures. Assuming the worst scenario of no more than 1 procedure for subjects, a maximum of 25 subjects needs to be enrolled. Anyway, the enrolment will stop when the total number of the procedures is reached.

12.4 Interim Analysis

No interim analysis is planned.

12.5 Dictionaries

Medical/Surgical history, concomitant diseases and AEs will be coded using Medical Dictionary for regulatory activities (MedDRA) dictionary and reported in separate tabulations. Frequency distributions and percentages will be summarized by System Organ Class (SOC) and Preferred Term (PT).

Prior and/or concomitant medications will be coded using World Health Organization Drug Dictionary and reported in separate tabulations. Frequency distributions and percentages will be summarized by Anatomical Main Group (1st level of the Anatomical Therapeutic Chemical (ATC) classification), Chemical Subgroup (4th level of the ATC classification) and Preferred Name.

13. ETHICS AND REGULATORY REQUIREMENTS

13.1 Approval

As a PMCF observational study conducted on a CE-marked medical device used according to its intended use with no additional procedure, this study doesn't fall within the scope of MDR 2017/745 nor French Jardé law on Research that implies human beings.

As Data Controller, the sponsor commits to comply with GDPR- 679/2016 and Title II Chapter 3 Section 3 of French Data Protection law of January 6th, 1978 regarding data processing.

According to Article 73 of French Data Protection law, considering that data processing related to this study complies with CNIL's reference methodology MR-004, for which the Sponsor, as Data Controller, has previously registered a compliance commitment with the French data protection body, authorization from CNIL is not mandatory for data processing and study start.

Sponsor has also submitted the study to APHP Research Ethical Committee.

13.2 Subject Information and Non-opposition

The screened patients, who has undergone JTIN implantation according to the standard-of-care and comply to all inclusion and exclusion criteria, should not oppose to participate in this study. Prior to being enrolled into the study, each patient, according to the age range, and his/her parents/legal representative, will be informed by the Investigator or his/her designee regarding the purpose of the study and the clinical data that will be collected. The Investigator will deliberate that, considering this is an observational study, there are no additional foreseeable risks and potential benefits resulting from study participation compared to normal clinical practice.

Each patient/parents/legal representative will be informed by the Investigator that he/she is free to refuse to participate in the study and, if he/she chooses to participate, that he/she may withdraw from the study at any time without providing reasons. In addition, the patient/parents/legal representative will be informed that, in some necessary cases, the Investigator may prematurely terminate their participation providing an appropriate reason.

The Investigator will provide the patient/parents/legal representative with her/his contact details in case they need further information after inclusion.

Each patient/parents/legal representative will be informed that his/her medical records will be Subject to review by the Sponsor representatives and may be subject to review from auditor and regulatory authorities.

The data collected during the treatment period, will be systematically entered by the investigator in eCRF.

The patients/parents/legal representative will be informed during their participation to the study about any new information eventually available about the medical device by the investigator.

Patient/parents/legal representative's non opposition will be documented in concerned patient's medical records and certified by Investigator or his/her designee.

13.3 Subject Confidentiality

All information and data concerning patients participating in this study will be considered confidential according to the requirements of EU GDPR regulations and national applicable regulations. The Information sheet shall describe the process of subject data protection in details.

Each enrolled subject will be assigned to a unique study ID number for each procedure, which is pre-configured in the EDC and all data collected in EDC will be identified only by this ID number. Records of the subject/study ID number relationship will be maintained only by the study center.

The study ID number is to be recorded on all study documents to link them to the subject's medical records at the site. To maintain confidentiality, the subjects' name or any other personal identifiers should not be recorded on any study document entered in EDC. In the event a subject's name is included for any reason, it will be blinded as applicable.

Confidentiality of data will be observed by all parties involved at all times throughout the study. All data shall be secured against unauthorized access. The privacy of each subject and confidentiality of his/her information shall be preserved in reports and when publishing any data.

14. STUDY MANAGEMENT AND ADMINISTRATION

14.1 Supplies

After the required approval will be obtained before the site will be initiated, the sponsor, also through its appointed partners, will provide the site with the following supplies:

- A paper and electronic copy of this protocol;
- Copies of the Information sheet to be provided to the enrolled Subjects;
- Blank copies of the non-opposition form to be signed by the Investigator or his/her designee;
- The Investigator Site File (ISF) containing all the study related documents;
- An eCRF platform and the credential to enter the system to upload clinical data.

14.2 Monitoring

The sponsor planned to perform a 100% source data verification (SDV) on inclusion/exclusion criteria and on the endpoints' variables, both primary and secondary. On the remaining data the SDV will be performed by random spot check (20% of the total visits entered in the eCRF). Before each visit the monitors will contact the investigator/center to schedule the visit and will send a written confirmation and the related agenda.

In order to fulfill its responsibility of assuring the proper conduct of the study regarding adherence to the protocol and the completeness and accuracy of the data recorded on the case report forms, the sponsor planned to perform at least the following monitoring visits:

- Site Initiation Visit (SIV), to be performed after EC/administrative approval;
- 4 monitoring visits throughout the life phase of the study;
- Close Out Visit (COV), after the last patient's data are entered into eCRF.

A detailed description of the monitoring activities will be provided in a separate Monitoring Plan. In case of need the investigational site is subjected to additional monitoring visits. The Investigator and/or study staff is expected to be available for at least a portion of the monitoring visit to answer to questions and to provide any missing information.

14.3 Direct Access to Source Data/Documents

With all efforts to ensure that patients' pseudo-anonymity and confidentiality is respected, the Investigator will permit the clinical monitors to have direct access to all study records, including hospital records, all source documents and ISF.

